Another potential mechanism favoring efficacy in preventing CHB, is that HCQ by virtue of reducing endosomal acidification might also decrease transplacental transport of maternal antibodies. This possibility is supported by the fact that maternal IgG is pinocytosed at the apical surface of the syncytiotrophoblast into an acid endosomal compartment containing FcRn, and migrates via transport vesicles to the basolateral surface of the cell, where at physiologic pH it uncouples from the receptor (15).

Study Design

Nineteen women in Stage 1 and an additional 51 women in Stage 2 (if reached, for a total of 70 subjects) meeting eligibility criteria will receive 400mg per day of HCQ beginning as soon as pregnancy is established and informed consent obtained. Mothers already on HCQ will remain on 400mg, or escalate to 400mg if on 200mg. The primary investigator, [name]., holds a U.S. Federal Drug Administration-issued IND (Investigational New Drug) number (112357) for HCQ.

A. Screening visit: Prior to the qualifying visit, the consent form will be reviewed and signed. Laboratory tests will include: CBC, liver-function tests (routine chemistries; albumin will be important to standardize the effect of physiologic hemodilution of pregnancy in gauging changes in autoantibody titers), urinalysis, and a 24 h collection for measurement of creatinine clearance and protein excretion as deemed appropriate. Serologic profiles will include: measurement of ANA, anti-DNA, C3 and C4. Blood will be drawn for baseline anti-Ro/La titer HCQ level, and IFNαactivity. Only the former will be available prior to qualification for enrollment. In total, 35 ml of blood will be drawn at screening.

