B. Qualifying Visit: This is done as soon as Ab status is established, which should take several days (ship overnight and assay in [name] laboratory is one day turnaround time; for [name], it is equivalent). A detailed history and physical examination will be performed. The patient will either be given a prescription for HCQ 200mg, 2 tabs hs, and advised to see an ophthalmologist, or told to maintain dose if 400mg. For women who have SLE, data will be collected to calculate the Systemic Lupus Erythematosus Pregnancy Disease Activity Index (SLEPDAI). Rheumatologists will complete assessment forms, which will be reviewed by Drs. [name] and [name] to address any effect of treatment on underlying SLE activity per se. Of note, [name] has provided these forms for use in the ongoing NIH-supported PROMISSE trial.

C. Follow-up Assessments: Fetal echocardiograms will be performed after enrollment (16-18 weeks) and weekly thereafter until 26 weeks, then biweekly until 34 weeks. Fetal echocardiographic scans will be performed according to standard methods [14,33,39], recorded on VHS videotape or DVD/Optical Disc by the pediatric cardiologist or obstetrician, and sent to the core echocardiographic lab and quantified on data abstraction forms by [name]. After the final fetal echo at 34 weeks, patients will continue with routine obstetric and rheumatologic care as appropriate. Neonates will have an EKG and echocardiogram at birth and at 1-year follow-up (it is acknowledged that this will be

out of the window of LFM award but not affect outcome since to date CHB has not occurred de novo after birth). Each woman will undergo routine obstetrical ultrasounds as per the treating obstetrician. Targeted Level 2 ultrasounds will be required between 21-24 weeks, and between 30-32 weeks to assess fetal well-being. Mothers enrolled in Europe will have their echocardiograms initially read by their primary cardiologists with the tapes then forwarded to [name].

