HCQ levels, This assay will be done in [name] laboratory in France. At each patient encounter, the interval between the last ingestion of HCQ and blood sampling is recorded. HCQ is assayed by HPLC with fluorometric detection as described [35] with minor modifications. The detection limit is 10ng/ml, and the between-day and within-day coefficients of variation are <8%.

IFNα activity: This assay will be done in [name] laboratory and will utilize the WISH cell assay, as we have previously reported in anti-Ro positive mothers of children with neonatal lupus [40].

The reporter WISH cells are incubated with 50% patient plasma or serum for 6 hours. Total mRNA is purified from WISH cell lysates and cDNA synthesized from total mRNAs. Forward and reverse primers are used for the genes MX1, PKR, and IFIT1, which are highly and specifically induced by type I IFN. The relative expression of each of the 3 tested IFN-induced genes is calculated as a fold increase compared to its expression in WISH cells cultured with media alone. The ability of patient serum to cause IFN-induced gene expression in the reporter cells is then compared to the mean and SD induced by healthy donor serum. The number of SD above the mean of healthy donors for each gene is calculated. Data are expressed quantitatively as the sum of the number of SD of each of the three genes above the mean of healthy donors. The 3 transcripts chosen for measurement represent coordinate activation of the IFN- α pathway as would be expected after ligation of the type I IFN receptor, instead of measurement of only one IFN- α -induced transcript which may not accurately represent pathway activation. Patients are considered to have high type I IFN activity if either of the two following criteria are met: 1) 2/3 tested IFN-induced genes are expressed >1 SD above the mean of healthy donors, and at least 1 is greater than or equal to 2 SD above the mean of healthy donors, or 2) 1 IFN-induced gene is expressed greater than 4 SD above the mean of healthy donor sera. If neither criterion is met, the sample is considered to have low type I IFN activity. Two-sided Fisher's exact test (sum of small p's method for observed \geq expected) is used to analyze the categorical data, and Mann-Whitney non-parametric t-test is used to compare quantitative data. All evaluations will be done in batch (with the exception of screening anti-Ro/La) when the patient has completed the study.

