Characteristics of the Research Population

Number of Subjects and Subject Recruitment

Stage 1, 19 subjects will be given HCQ. If fewer than 3 recurrences are observed, an additional 51 subjects will be treated in Stage 2 (Years 2-3, seeking a renewal and/or NIH funding). However, if 3 or more recurrences are observed after Stage 1, it will be concluded that HCQ is not effective in preventing CHB. Ultimately, HCQ will be considered efficacious for CHB if fewer than 6 CHB cases occur among 70 subjects evaluated on no potentially confounding medications.

While some subjects will be prescribed the study drug (HCQ) by the PI, [name], or a designated study team member (covered by Consent Form Version 1), many patients will be referred to the study from other sites. In these cases, patients' own doctors will take responsibility for prescribing the study drug, and patients will consent to have their bloods and medical records sent to the investigators at NYU for data and sample analysis (as delineated in Consent Form Version 2). [name] or another study team member will discuss the study with each potential subject and complete the informed consent process prior to enrollment. All subjects (74 in total) will be considered enrolled at NYU and consented using NYU IRB-approved consent forms.

Gender of Subjects

Because the aim of this study is to determine whether hydroxychloroquine use during pregnancy prevents congenital heart block, only female subjects will be recruited.

Age of Subjects

18-45

Racial and Ethnic Origin

No subject will be excluded from participation in this study on the basis of race or ethnic origin.

Eligibility (Inclusion) Criteria

1) Mothers must have anti-Ro and/or anti-La Ab documented in the NYU immunology laboratory (CLIA-approved), which utilizes an ELISA (Immunovision) as well as reactivity on ELISA to at least one of three recombinant antigens (48La, 52Ro, 60Ro, JB laboratory). [name] will likewise

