verify Ab in his laboratory. 2) Mothers must have a previous child with cardiac NL, defined herein as: the presence of heart block (1st, 2nd, or 3rd degree) documented by electrocardiogram (EKG), echocardiogram, pacemaker, or statement in the medical record, and/or; presence of cardiac injury, which specifically includes autopsy evidence of a mononuclear infiltrate in the endocardium, myocardium, and pericardium and/or EFE on echocardiogram always associated with cardiac dysfunction. In PITCH, we included women with a prior child with rash; however, recent data generated from the RRNL suggest that recurrence of CHB following rash is 11%, not 18% [34]. Thus, inclusion of previous rash could lead to a falsely lowered recurrence rate, and will therefore be excluded. 3) Intrauterine pregnancy \leq 12 weeks. 4) Mother may be taking \leq 20 mg prednisone because, in our experience, CHB has developed in the presence of this dose. 5) Mother may be asymptomatic, or have a rheumatic disease such as SLE or SS. Maternal health status has not been considered an influence on the development of CHB [1]. 6) Mother may or may not already be taking HCQ. This latter point was discussed with [name], who has published extensively on measurement of HCQ [35,36]. While it might be optimal for the mothers anticipating enrollment in the study to all have been on HCQ prior to conception, this is impractical. Some may never achieve pregnancy and not want to take HCQ unless they conceive (especially those asymptomatic). On the other hand, women with SLE are likely to already be on HCQ and it would limit enrollment to exclude these patients if all must initiate HCQ only at enrollment in the first trimester. Although the accepted dogma is that HCQ requires several months for maximal efficacy in treating rheumatic disease, it is unknown whether this would apply to transplacental passage or fetal levels (which are impossible to measure). [name] suggests that HCQ is probably a three compartment model which includes the circulation, tissues and cells. In the circulation, the half life is approximately 7 days and in the tissues, it is 40 days [37,38]. In [name] experience, steady state blood levels of HCQ are achieved in 4-6 weeks. Thus, dosing the mother no later than 10 weeks gestation should provide sufficient fetal exposure before the vulnerable period of CHB which is generally accepted to span 18-24 wks. Furthermore, the placenta has to be formed for HCQ to gain access to the fetus and it may be effective quickly for the biology we are considering.

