The proposed design has the following operating characteristics. Let p1 = recurrence rate definitely not worthy of further investigation; p2 = recurrence definitely worthy of further investigation. In this study, we define p1 = 18% [41] and p2 = 5%. According to Simon's optimal 2stage approach [32], the expected sample size is 29.8 subjects with a probability of early termination of 0.69 when the recurrence rate is equal to p1. The probability of accepting the treatment for further study is at most 5% if the recurrence rate is unacceptably high (>18%) with that treatment. In contrast, there is a 90% probability of accepting the treatment for further study if the true recurrence rate is 5%. It is important to emphasize that the purpose is to obtain critical data on the efficacy of HCQ in the prevention of recurrent CHB and determine whether this preventive approach should be studied further. At study completion, the proportion of mothers having a child with advanced CHB will also be computed, along with corresponding 95% confidence intervals. Secondary endpoints that are binary (i.e., occurrence of 1st degree block, abnormal fluid collection) will be analyzed by similar approaches. Continuous variables (e.g., shortening fraction, gestational age) will be summarized by estimating means and standard deviations. The effect of therapy on HCQ levels, IFN-α signatures, and Ab titers will be evaluated by fitting mixed effects linear models to repeated assessments of titers obtained during follow-up. In addition, change in any of these analytes at specific time points from baseline will be analyzed using the paired t-test or Wilcoxon signed rank test, depending on distribution of the data.

Safety committee. An independent DSMB will convene by teleconference three times during the year. The members include Drs. [name], [name], and [name] (all of whom served in PITCH).

Data Storage and Confidentiality

Data management. Study information will be recorded at the patients' obstetrical and rheumatology sites. Standardized, computer-adapted case report forms (CRFs) have been developed. Within 2 weeks of each visit, completed CRFs and tapes of the echocardiograms will be sent to [name]. Following review, CRFs will be faxed to the coordinator at NYU for final error checks and entered into the computer database. The coordinator will maintain a calendar for each patient, monitor completion

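### The baseline anti-Ro/La titre is assayed in real time, outside the batch used for later titres, so the paired change from baseline mixes assay differences with any drug effect

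*Combined protocol and SAP*

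**What the plan says.** - **Source of the baseline.** Study Design, A. Screening visit, takes the baseline titre, HCQ level and IFNα activity from the screening draw ("Blood will be drawn for baseline anti-Ro/La titer HCQ level"). Of these only the titre is read before enrolment: "Only the former will be available prior to qualification for enrollment".
- **Speed of the screening assay.** B. Qualifying Visit describes it as "ship overnight and assay in [name] laboratory is one day turnaround time; for [name], it is equivalent".
- **Timing of everything else.** The IFNα activity paragraph ends: "All evaluations will be done in batch (with the exception of screening anti-Ro/La) when the patient has completed the study".
- **Analysis.** Data Analysis And Data Monitoring plans mixed models for repeated titres during follow-up and adds that "change in any of these analytes at specific time points from baseline will be analyzed using the paired t-test or Wilcoxon signed rank test". No run or laboratory term is mentioned. The only standardisation described for titre is albumin, for haemodilution (Screening visit).
- **Method.** Evaluation of Ab Levels uses a recombinant Ro60, Ro52 and La48 ELISA and refers to the IVIG trial for details.
- **Laboratories.** Inclusion criterion 1 begins "Mothers must have anti-Ro and/or anti-La Ab documented in the NYU immunology laboratory (CLIA-approved" and adds that another investigator will "verify Ab in his laboratory".
- **Storage.** C. Follow-up Assessments lists four sampling visits, starting with screening. It has serum banked in aliquots at -70°C and European samples stored and shipped in batch.

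**The concern.** A paired test assumes that both members of the pair were measured on the same scale. Here the first member is a rapid assay of recently drawn serum. The second is run months later on stored serum in a different session. Lot drift, storage or a change of laboratory could move one against the other.

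Baseline HCQ and IFNα fall inside the batch, so the problem is confined to titre. With no control group, a persistent assay shift has nothing to be compared with and would be read as a change on therapy. It could equally hide a real change. Titre is one of the three analytes on which the plan says it will evaluate the effect of therapy.

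**Working it through.** **Plan's own figure.** The documents give no sample size, power or precision for the titre analysis, so there is nothing to reproduce. The only assay variation stated (below 8%) belongs to the HCQ assay.

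**Inputs from the documents.** N = 19 (Stage 1) and N = 70 (both stages); one arm; paired t-test on change from baseline.

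**Assumed inputs.** Two-sided 5% test; no drug effect; a persistent shift of 10%, 15% or 20% between screening and batch assay, shared by all women; SD of the within-woman log-change of 0.3 or 0.6.

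**Case 1: persistent shift.** The paired t statistic is noncentral t with N−1 degrees of freedom and noncentrality ln(1 + shift) × √N / SD. The false-positive rate is the probability that |t| exceeds the critical value (2.101 at N=19, 1.995 at N=70).

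The log-shifts are ln 1.10 = 0.0953, ln 1.15 = 0.1398 and ln 1.20 = 0.1823. For example, at 10%, SD 0.3 and N=19 the noncentrality is 0.0953 × √19 / 0.3 = 1.385, and the rejection probability is 0.259.

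| SD of log-change | N | 10% shift | 15% shift | 20% shift |
|---|---|---|---|---|
| 0.3 | 19 | 26% | 49% | 71% |
| 0.3 | 70 | 75% | 97% | >99% |
| 0.6 | 19 | 10% | 16% | 24% |
| 0.6 | 70 | 26% | 49% | 71% |

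**Case 2: purely random offsets.** Suppose each woman's screening run and batch run have independent mean-zero offsets with SD s, in units of the SD of the change. The variance of the change rises from 1 to 1 + 2s², so the standard error is multiplied by √(1 + 2s²): 1.06, 1.22 and 1.73 for s = 0.25, 0.5 and 1.0. The mean is not biased, and in simulation the false-positive rate stayed at 5%. The cost is lost precision.

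**Case 3: shift in a subgroup only.** If about 30% of women (6 of 19, or 21 of 70) carried a shift of 0.5 SD of the change, simulation gives false-positive rates of 9% at N=19 and 22% at N=70. For a shift of 1.0 SD the rates are 20% and 63%. The 30% share is an assumption.

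**After the fix.** If baseline and follow-up sera share a run and a laboratory, the common offset cancels in the difference and the rate returns to 5%.

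**The case against.** The strongest reply has four parts.

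1. *The exception may concern timing only.* Screening cannot wait for the batch, and the text does not say that banked screening serum is left out of the later run. The IVIG-trial method it refers to may include a re-run. This is possible, but the protocol calls the screening titre the baseline, states the exception, and mentions no re-assay, bridging sample or common calibrator. If a re-run is the practice, one sentence would settle the matter.

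2. *Run effects average out.* Batching is described per patient and screening is spread over enrolment, so offsets may differ from woman to woman. This stands for random offsets (Case 2). It does not cover a one-directional difference such as fresh versus stored serum. The documents neither show nor rule out such a difference.

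3. *The size rests on an assumed SD.* This stands. Doubling the SD cuts the N=19 range from 26–71% to 10–24%.

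4. *The analysis is peripheral.* Titre is not the primary outcome or one of the eight listed secondary outcomes, and it enters neither the stopping nor the efficacy rule. Comparisons among a woman's batched follow-up samples are sound. Haemodilution and prior HCQ use already make the paired change hard to attribute to the drug. All of this stands and limits the weight of the point.

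A reader might also infer that European women are screened in a different laboratory from the one that runs their later samples. The documents suggest a second antibody laboratory but do not say so: the names are removed, criterion 1 asks for NYU documentation, and no visible text ties the other laboratory to European enrolment. Nor is European batch shipment limited to later samples. Following the list of visits that begins with screening, it appears to include the screening sample.

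**Conclusion.** The point holds for the titre analysis. As written, the baseline titre comes from a different assay session from every later titre, and the paired tests carry no correction for this. Random run offsets would widen the standard error. A persistent shift would bias the mean change and could not be separated from a drug effect in this single-arm design.

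The direction and size of any bias cannot be determined from the documents. The false-positive rates above are illustrations that depend on a shared shift and an assumed SD. A second screening laboratory would be a further source of shift if one is used, but the conclusion does not need it. The trial's main conclusion about recurrence of heart block is not at risk. This is a cheap improvement worth making to a biomarker analysis.

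**What to change.** State in the protocol that the rapid screening result serves eligibility only. For the change analysis, re-assay a banked screening aliquot for Ro60, Ro52 and La48 in the same laboratory and run as that woman's later samples. Define that value as baseline for the paired tests and for any model that uses baseline. For European women, confirm that the screening aliquot is part of the stored and shipped batch. If the re-run is already the practice, say so.

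The cost is one extra sample per woman on plates already being run and a sentence or two of text. Provided an aliquot of the 35 ml screening draw is banked, no extra blood or visit is needed. The change removes shared run and laboratory offsets. It does not by itself turn a change from baseline into a drug effect, since haemodilution and prior HCQ use remain.

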With over 400 families now enrolled in the RRNL and our success at rapid enrollment in PITCH, we are well positioned to enroll in the current study. Most of the women enrolled in the RRNL are of childbearing age, motivation is quite high, and based on review of overall data, it is likely that at least 20% will again become pregnant and available for this study. Importantly, PRIDE and PITCH solidified a referral base of obstetricians and pediatric cardiologists. Furthermore, [name] has agreed to participate given that all 19 patients must be recruited in one year. The DSMB for the U.S. based PITCH study ([name], maternal-fetal medicine, [name], rheumatologist with expertise in pregnancy and women's health issues, and [name], rheumatologist with expertise in design and monitoring of clinical trials in SLE) in conjunction with Drs. [name], [name], [name] (pediatric cardiologist), and [name] (statistician) have had extensive discussions regarding the results of PITCH and the design of this current study. With regard to a randomized trial comparing any drug with placebo, [name] prepared the following analysis:

Assumptions 1. Recurrence rate of CHB (whether previous child had CHB or rash) is approx 19%.

2. Clinically meaningful outcome would be at least 50% reduction in recurrence rate.

Power Calculations 19% to 10% recurrence rate: 261 per group (N = 522)

19% to 5% recurrence rate: 97 per group (N = 194)

Data Analysis And Data Monitoring

Statistical considerations for overall study:

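### Three recurrences in 19 justify not taking HCQ forward, but not the stated conclusion that it is ineffective: a drug that halves recurrence would get that label about 24% of the time

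*Combined protocol and SAP*

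**What the plan says.** All places are in the combined protocol and SAP.

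- **Study Design** sets the size: "Nineteen women in Stage 1 and an additional 51 women in Stage 2", 70 in all.
- **Number of Subjects and Subject Recruitment** attaches a conclusion about efficacy to the interim boundary. At 3 or more recurrences in Stage 1, "it will be concluded that HCQ is not effective in preventing CHB". For the final analysis it states only the favourable side: "HCQ will be considered efficacious for CHB if fewer than 6 CHB cases occur among 70 subjects". It gives no explicit conclusion for 6 or more.
- **Statistical considerations for overall study** sets the two rates: "we define p1 = 18% [41] and p2 = 5"%. It reports operating characteristics at those two rates only. At recurrence above 18%, "The probability of accepting the treatment for further study is at most 5"%. At the other end, "there is a 90% probability of accepting the treatment for further study if the true recurrence rate is 5"%. The same paragraph describes the aim as deciding whether the approach merits further study, and it plans a 95% confidence interval for the rate of advanced block.
- **Methods and Procedures**, in an analysis of a possible randomized comparison of any drug with placebo, takes a recurrence rate of about 19% (previous child with CHB or rash) and states: "Clinically meaningful outcome would be at least 50% reduction in recurrence rate".
- **Specific Aim** describes the Stage 1 outcome more neutrally, as termination after the first stage. It also says that the study's results should inform the counselling of women with these antibodies.

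**The concern.** A Simon two-stage rule yields a go or no-go decision. It separates a rate not worth pursuing (18%) from one clearly worth pursuing (5%), and rates in between may fall either way. The statistical section respects this, because its probabilities are about accepting the treatment for further study. The recruitment section does not: it turns the interim no-go into a finding that the drug does not work.

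The distinction matters here because the plan calls a reduction of at least half clinically meaningful, whereas the design targets 18% to 5%, a reduction of 13/18 = 72%. Nothing in the plan tells the reader how often a drug that halves recurrence would be turned away. The condition carries a stated mortality of 20-30% and the results are meant for counselling, so an overstated negative could reach patients.

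**Working it through.** **Inputs.** Stage 1 n = 19, stop at 3 or more; total N = 70, success at 5 or fewer; p1 = 18%, p2 = 5% (sections cited above). The intermediate rate is half of 18% = 9%. As a sensitivity check I use half of 19% = 9.5%, and the 10% in the plan's own randomized-trial calculation. Women are treated as independent with a common rate, and all 19 as evaluated before Stage 1 is judged.

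**Formulas.**
- Stage 1 stop: S(p) = 1 − Σ Bin(x; 19, p), x = 0, 1, 2.
- Acceptance: A(p) = Σ Bin(x; 19, p) × P[Bin(N − 19, p) ≤ 5 − x], x = 0, 1, 2.
- Failure of the whole rule: 1 − A(p).
- Expected size: 19 + (1 − S)(N − 19).

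**Step 1: the plan's own figures.** The plan states early termination 0.69 and expected size 29.8 at 18%, error at most 5%, and 90% acceptance at 5%.

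| | Stated | N = 70 | N = 54 |
|---|---|---|---|
| Early termination at 18% | 0.69 | 0.691 | 0.691 |
| Expected size at 18% | 29.8 | 34.8 | 29.8 |
| Acceptance at 18% | at most 5% | 0.75% | 4.9% |
| Acceptance at 5% | 90% | 83.2% | 90.3% |

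The expected size and the 90% belong to a total of 54 with the same boundaries, not to the 70 in the text. That conflict is a separate matter, but it affects the figures below, so both totals are shown.

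**Step 2: what a Stage 1 stop shows.** 3/19 = 15.8%, with a Clopper-Pearson 95% interval of 3.4% to 39.6%. The interval contains 5%, 9% and 18%. The result that triggers the conclusion of inefficacy is therefore compatible with the full target effect, with a halving, and with no effect.

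**Step 3: how often a halving drug meets that label.** At 9%, the probabilities of 0, 1 and 2 recurrences in 19 are 0.1666, 0.3131 and 0.2787 (unrounded sum 0.7585). So S = 1 − 0.7585 = 0.2415. At 9.5% it is 26.8% and at 10% it is 29.5%. At the 5% target it is 6.7%.

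**Step 4: the whole rule at 9%.**
- N = 70: 0.1666 × 0.6910 + 0.3131 × 0.5099 + 0.2787 × 0.3151 = 0.115 + 0.160 + 0.088 = 0.363. Failure is 63.7%, of which 24.1 points come from Stage 1 and 39.6 from missing the final boundary.
- N = 54: 0.1666 × 0.9100 + 0.3131 × 0.7968 + 0.2787 × 0.6122 = 0.152 + 0.249 + 0.171 = 0.572. Failure is 42.8%.
- With N = 70, failure is 68.8% at 9.5% and 73.4% at 10%.

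**Step 5: the final boundary.** 6/70 misses the success rule, yet it is 8.6%, less than half of 18%. Its ordinary exact interval, 3.2% to 17.7% (not adjusted for the two stages), lies below 18%. Reading that result as no effect would contradict the interval that the plan promises to report.

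**The case against.** Four points can fairly be made for the plan.

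1. *Low acceptance between the two design rates is inherent in a Simon design.* This stands. The thresholds and the choice of 5% as the target are not at fault; the objection is to the label put on a negative result.
2. *The 50% criterion was not set for this trial.* This stands in part. It appears in the discussion of a randomized trial, with a base rate of about 19% that includes women whose previous child had only a rash, a group this trial excludes. Applying it to 18% is my step. It remains the plan's only statement of what is clinically meaningful, and using 19% makes the figures less favourable.
3. *The purpose is already stated correctly and a confidence interval is planned.* True. No new analysis is needed, and the contradiction lies between two sections of the same document.
4. *The 90% is expressly conditional on a true rate of 5%.* Also true; the sentence does not claim power at any other rate.

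A reader might go further and infer that a drug that halves recurrence would usually be declared ineffective, citing the 64%. The documents do not support that. The conclusion of inefficacy is attached to the Stage 1 boundary only, which such a drug escapes about 76% of the time. For 6 or more of 70 a negative conclusion is at most implied. Part of the 64% also comes from keeping a limit of fewer than 6 with 70 subjects; with 54, a halving drug would be accepted more often than not (57%). Likewise, the 17% failure at a true 5% (1 − 0.832) reflects the 54-versus-70 conflict and is not additional evidence here.

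**Conclusion.** The point holds as one of wording and disclosure. The Stage 1 rule states a conclusion that the design cannot support and that its own statistical section does not claim. The probability tied to that wording is about 24% for a drug that halves the 18% rate, and 27% to 29% if the halving starts from 19%. The 64% (43% with 54 subjects) measures something else, failure of the whole rule, and should be quoted only as that.

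These figures rest on the binomial model above and on reading the three-case stop as a Stage 1 rule. The study stopping rules under Protection Against Risks halt enrolment at three affected fetuses without limiting this to Stage 1. Read literally over 70 women, that limit would be reached 95.7% of the time at a true 9%. The two passages must be reconciled; the figures here follow the recruitment section.

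**What to change.** 1. Under Number of Subjects and Subject Recruitment, replace "it will be concluded that HCQ is not effective in preventing CHB" with wording such as: *HCQ will not be taken forward under this design; a reduction smaller than to 5% is not excluded.* Use the same wording for 6 or more recurrences at the final analysis, where the plan is now silent. The planned confidence interval then shows which rates remain compatible with the data.
2. Settle whether the total is 54 or 70. Then state acceptance at both 5% and 9% for the confirmed size: 83% and 36% for 70, or 90% and 57% for 54. The 9% figure should not be added before this is settled, because 36% beside the present 90% would mix two designs in one sentence.

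The cost is a few sentences. This point itself asks for no change to thresholds, conduct or analysis. The drawback is that the stated operating characteristics will look less favourable.
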